9.7 Analysis of Safety Data

Safety data as outlined in [Section 8](#) will be summarized by treatment group for both mothers and infants. Summary statistics will be prepared for measured values and changes from baseline values for each dose group. No statistical inference testing will be performed on the safety data.

Adverse events will be coded using the Medical Dictionary for Regulatory Activities (MedDRA) coding dictionary and summarized by relatedness, intensity, and seriousness. AEs may also be summarized by other factors such as gestational age or intensity of baseline preeclampsia symptoms. Summaries of the adverse event data will be completed for all subjects. Summaries of the number and percentage of subjects with at least one treatment emergent AE, classified according to preferred term and/or body system using the MedDRA dictionary, will be provided overall and by treatment group for:

- Overall summary
- All treatment-emergent AEs
- Treatment-emergent AEs by relationship (probably not related, possibly related, probably related)
- Treatment-emergent AEs by intensity (mild, moderate, severe)
- SAEs
- Treatment-emergent AEs leading to withdrawal from the study

Heart rate, systolic and diastolic blood pressure, temperature, respiratory rate, and pulse oximetry versus time data will be summarized by treatment group with descriptive statistics at each scheduled time point. Individual and mean values versus time profiles will be provided for each treatment group. Summaries of treatment-emergent clinically important abnormalities in vital sign and laboratory data will be provided. No inferential statistical analysis is planned.

Clinically significant new abnormal findings of vital signs or clinical laboratories will be reported as adverse events.

Laboratory parameters, vital sign data, and weight will be summarized by treatment group and presented in tabular and graphic formats where appropriate. Appropriate cross-tabulations will be provided to detect any significant changes in laboratory parameters, vital sign values, or weight but no formal statistical tests are planned.

9.7.1 Other Maternal Outcomes of Special Interest

The following maternal outcomes will be analyzed:

- Renal function – Change from baseline to all assessment time points in measurements of blood urea nitrogen (BUN), serum creatinine, and urine electrolytes.
- Hepatic function – Change from baseline to all assessment time points in measurements of alanine aminotransferase (ALT), aspartate aminotransferase (AST), and total bilirubin.
- Platelet count – Change from baseline to all assessment time points.
- Pulmonary edema – Defined as either of the following in which cardiovascular causes or magnesium toxicity have been clinically excluded:
 - a. Chest X-ray consistent with pulmonary edema, or
 - b. New onset hypoxemia (room air SpO₂ less than or equal to 94%) in association with tachypnea.

- HELLP (hemolysis, elevated liver enzymes, low platelet count) syndrome
- Placental abruption
- Delivery latency
- Percent progression to HELLP
- Percent progression to eclampsia

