7.2 Screening / Baseline

Screening assessments may be completed up to 24 hours prior to the first planned dose of study drug.

Assessments collected at time of hospital admission, but prior to consent, e.g., labs and biophysical profile, may be used as baseline assessments, as long as these assessments were completed within the protocol required timeframe.

The following screening procedures will be performed:

- Signed informed consent
- Inclusion/exclusion criteria
- Complete medical history / pregnancy history / demography
- Physical examination, including mental status examination
- 12-lead electrocardiogram (ECG)
- Height and weight
- Clinical chemistry (including serum creatinine), hematology, and urinalysis. Abnormal clinical lab test results may be repeated once for confirmatory purposes. See [Appendix 3](#).
 - Screening urinalysis should include electrolytes, as much as possible. See [Appendix 3](#).
- Vital signs (blood pressure, heart rate, respiratory rate, body temperature, and pulse oximetry) measurements. For ambulatory subjects, vital signs should be measured after approximately 5 minutes of quiet rest with the subject comfortably seated, legs uncrossed, back and arm supported with the middle of the cuff on the upper arm. For non-ambulatory subjects, vital signs should be measured in a semi-reclined position.
- Preeclampsia symptom assessment – list of preeclampsia symptoms is included as [Appendix 4](#)
- Modified early obstetric warning score (MEOWS) – [Appendix 5](#)
- Biophysical profile
- Fetal heart monitoring
- Blood sample collection for anti-AMAG-423 antibody concentration (i.e., immunogenicity)
- Blood sample collection for assay development
- Prior / concomitant medication record
- Initiate adverse event monitoring

Screening assessments will be used as baseline assessments in the efficacy/safety analyses evaluating change except where indicated below:

- If screening clinical labs are collected greater than 6 hours prior to dosing, an additional blood sample should be collected for chemistry and hematology and an additional urine

sample should be collected for urinalysis prior to dosing. Results must be obtained prior to randomization and dosing.

- Vital signs should be collected just prior to dosing (within 1 hour of dosing).

All subjects who are screened but do not meet eligibility criteria or who decline to participate should have the reason for screen failure documented.

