If corticosteroid administration (betamethasone or dexamethasone) and magnesium sulfate administration have not been initiated/completed by this time, it should be initiated as per standard of care at the individual site. If clinically appropriate, blood samples may be drawn from a central line, by venipuncture, or by a peripheral catheter.

7.3 Treatment Period – Days 1 – 4

The treatment period will begin with the first dose of study drug and end six hours following the last dose of study drug (i.e., a period of 96 hours for subjects completing the full course of treatment) or at the time of delivery if sooner. During the treatment period subjects will be administered study drug every six hours for a maximum total of sixteen doses. Efficacy and safety evaluations and blood samples for PK evaluations will be performed/obtained as noted in [Sections 7.3, 7.4, 7.5, and 7.6](#) below. If a subject goes into labor during the treatment period, study drug will be continued, as much as possible, until delivery. Similarly, efficacy and safety evaluations will be completed up to delivery, as much as possible. If delivery occurs during the treatment period, as much as possible, study assessments should be conducted prior to delivery if ≥ 12 hours have elapsed since the previous collection.

For study purposes, standard of care assessments will not be captured unless there are clinical findings.

- Randomization
- Study drug administration – Every 6 hours x 4 days (16 doses)
- Mental status exam and brief physical exam – should be completed per standard of care, and/or minimally, once a day, starting approximately 24 hours after the first dose. As much as possible, mental status and brief physical exams should be completed 24 hours apart.
- Weight – collected per standard of care.
- ECG – completed per standard of care.

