- Fetal heart rate monitoring – 24-hour continuous fetal heart rate monitoring (to be initiated at start of first dose) until 24 hours post first dose. For the remainder of the treatment period, continuous fetal heart rate monitoring should be conducted for one hour after initiation of each dose, unless additional fetal heart rate monitoring is clinically indicated. Clinically significant abnormal findings along with category designation (e.g., III) from fetal heart rate monitoring must be recorded. If continuous fetal heart rate monitoring is difficult or not possible due to subject's weight and/or fetal gestational age, attempts to obtain several one hour strips on Day 1 of treatment should be made documenting why continuous fetal heart rate monitoring is not possible.
- Biophysical profile – completed per standard of care.
- Laboratory assessments (clinical chemistry, hematology, and urinalysis), including serum creatinine – should be collected 24 hours after the first dose (± 2 hours) and then per standard of care, and/or minimally, once a day. As much as possible, labs should be collected 24 hours apart.
 - Urinalysis conducted 24 hours after the first dose should include electrolytes, as much as possible, and then SOC. See [Appendix 3](#).

- A full set of vital signs (i.e., blood pressure and heart rate, respiratory rate, body temperature, and pulse oximetry) – should be collected every 4-6 hours after first dose, as much as possible.
- Preeclampsia symptom assessment – should be collected per standard of care, and/or minimally, once a day, starting approximately 24 hours after the first dose. See [Appendix 4](#).
- MEOWS – should be conducted 24 hours after the first dose (± 2 hours) and then once a day. As much as possible, MEOWS should be completed 24 hours apart. See [Appendix 5](#).
- Adverse event record
- Concomitant medication record
- AMAG-423 PK blood sample collection and blood sample collection for assay development per the following table, as much as possible:

Dosing time (hour administered)	Sample Time			
	Pre-dose	End of infusion**	3 hours post dose	6 hours post dose
0	X*	X	X	X
24	X	X		
90***	X	X	X	X

*One sample collected as soon as possible after consent and a second sample just prior to dosing for assay development. One sample collected for AMAG-423 PK analysis.

**End of infusion samples should be obtained at or just prior to stopping the infusion pump

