8.2 Safety Assessments

Safety assessments for the mother and fetus/infant will be collected.

Maternal assessments will include vital signs (blood pressure, heart rate, respiratory rate, body temperature, and pulse oximetry), body weight, mental status exams, physical examinations, clinical laboratory tests (chemistry, hematology, and urinalysis), immunogenicity analyses, MEOWS, preeclampsia symptom assessment, and adverse events. The schedule of these safety assessments has been discussed in the Study Procedures section above and is provided in [Appendix 1](#).

Fetal/infant assessments will include fetal heart tracing, biophysical profile (fetal breathing movements, gross body movements, tone, reactive heart rate and qualitative amniotic fluid), infant outcome assessment, cord blood assessment if available (arterial cord gas pH and base excess/base deficit), cranial ultrasound, infant exam (weight, length, and head circumference), immunogenicity analysis, and adverse events.

For study purposes, standard of care assessments (e.g., ECG, infant labs) will not be captured unless there are clinical findings, at which point they will be captured as adverse events.

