Appendix 3: Clinical Laboratory Testing – Maternal

Chemistry	Hematology	Urinalysis
Albumin	Hematocrit	Bilirubin
Alkaline phosphatase	Hemoglobin	Blood/RBCs
ALT	Mean cell volume (MCV)	Color
AST	Mean corpuscular hemoglobin (MCH)	Glucose
Bicarbonate or CO ₂	Mean corpuscular hemoglobin concentration (MCHC)	Ketones
BUN	Mean platelet volume (MPV)	Leukocytes or WBCs
Calcium	Platelet count	Microscopic exam
Chloride	Red blood cell count	Nitrite
Creatinine	White blood cell count	pH
Glucose	White blood cell (WBC) differential (basophils, eosinophils, lymphocytes, monocytes, and neutrophils) – both absolute count and percentages	Protein
Lactate dehydrogenase (LDH)		Specific gravity
Magnesium		Urobilinogen
Potassium		Electrolytes (sodium, potassium, chloride, calcium, and creatinine)*
Sodium		
Total Bilirubin; if elevated obtain direct bilirubin		

*Urine electrolytes to be collected at Screen and 24 hours after first dose, as much as possible, and then standard of care.

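### Section 9.7.1 summarises urine electrolytes at every time point without correcting for urine concentration, although urine creatinine is in the same panel and values after 24 hours are captured only selectively

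*Combined protocol and SAP*

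**What the plan says.** Under renal function, Section 9.7.1 lists "Change from baseline to all assessment time points in measurements of blood urea nitrogen (BUN), serum creatinine, and urine electrolytes". It mentions no creatinine ratio, fractional excretion or timed excretion.

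The urine panel in Appendix 3 reads "Electrolytes (sodium, potassium, chloride, calcium, and creatinine", so urine creatinine comes from the same specimen. The chemistry panel in that appendix holds the serum counterparts. The electrolytes are part of the urinalysis, and the schedule in Appendix 1 contains no timed urine collection.

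On collection:
- Section 7.2: "Screening urinalysis should include electrolytes, as much as possible".
- Section 7.3: "Urinalysis conducted 24 hours after the first dose should include electrolytes, as much as possible, and then SOC".
- Appendix 3, footnote: "Urine electrolytes to be collected at Screen and 24 hours after first dose, as much as possible, and then standard of care".

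On capture, Sections 7.3 and 7.4 both state: "For study purposes, standard of care assessments will not be captured unless there are clinical findings". Section 8.2 adds that such assessments "will not be captured unless there are clinical findings, at which point they will be captured as adverse events".

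On inference, Section 9.7, which contains 9.7.1, states: "No statistical inference testing will be performed on the safety data".

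**The concern.** There are two separate weaknesses.

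First, the concentration of an electrolyte in a single urine specimen depends on how dilute the urine is as well as on how much is excreted. Hospitalised women with severe preeclampsia can differ widely in urine flow. IV fluids are recorded on the routine-medication checklist (Section 7.8, Appendix 8), and the document does not say that volume is recorded. Adjusting for fluids afterwards would therefore be difficult, whereas urine creatinine is already measured and would remove dilution directly.

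Second, the analysis promises more time points than collection can supply. After 24 hours an electrolyte value reaches the database only if someone ordered it and there was a clinical finding, and then possibly as an adverse event without a number. A summary of such values would be selected on the result.

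What is at stake is modest but specific to this drug. The proposed mechanism is reversal of Na+/K+-ATPase inhibition (Section 4). The placental and cord ATPase samples are optional, limited to US sites and kept for future analysis (Section 7.6). Urine electrolytes are therefore the only urinary measure of sodium handling scheduled across all sites.

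**Working it through.** The plan gives no sample size, SD or power for this outcome, so there is no figure to reproduce. The check has three parts.

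**1. Collection against analysis.** Section 7.9 implies up to nine maternal laboratory occasions: screening (1), Days 2–5 (4), and 24 hours post final dose, 24 hours postpartum, discharge and 6 weeks (4); 9 × 12 mL = 108 mL, as stated there. Urine electrolytes are scheduled at two of these, screening and 24 hours after the first dose. For the other 9 − 2 = 7, a urinalysis is due but the electrolytes are standard of care, under the restricted capture rule. Section 9.7.1 makes no such distinction.

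**2. Algebra of dilution.** With urine flow V, urine X = (excretion of X)/V and urine creatinine = (excretion of creatinine)/V. The ratio is (excretion of X)/(excretion of creatinine), and V cancels. If flow doubles with excretion unchanged, an assumed urine sodium of 100 becomes 50, urine creatinine also halves, and the ratio is unchanged.

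**3. Size of the effect between arms (illustration).** The 100 per arm is from Section 9.3; every other input is assumed. Log electrolyte concentration = e + d, where e is log excretion relative to creatinine (SD 0.35, within-woman correlation 0.5) and d is log concentration due to dilution (SD 0.3 to 0.7, independent between visits). The baseline geometric mean is 100. The outcome is 100 × [exp(x at 24 h) − exp(x at baseline)], averaged by arm and differenced, active minus placebo, over 2,000 simulated trials. For the measured concentration x = e + d; for the corrected value x = e.

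| Log-SD of dilution | Measured, no effect, equal dilution | Measured, no effect, active urine more dilute by 0.2 log | Measured, true effect +0.2 log (SE) | Corrected, true effect +0.2 log (SE) | SE ratio |
|---|---|---|---|---|---|
| 0.3 | +0.2 | −19.9 | +24.8 (9.84) | +23.6 (5.86) | 1.7 |
| 0.5 | +0.2 | −21.8 | +26.1 (15.82) | +23.5 (5.87) | 2.7 |
| 0.7 | −0.4 | −24.4 | +29.6 (25.22) | +23.7 (5.85) | 4.3 |

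- With equal dilution in the arms, the difference is about zero and a nominal 5% test rejects in 4% to 5% of runs. Dilution is then noise, not bias.
- If one arm's urine is more dilute by 0.2 log (1 − exp(−0.2) = 18%), the measured difference moves by 20 to 24 on a baseline of 100, with no change in excretion relative to creatinine.
- The SE ratios treat urine creatinine as a perfect measure of dilution. Real variation in creatinine excretion would reduce the gain.

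For capture after 24 hours, suppose only values below −0.6 log are kept (exp(−0.6) = 0.55 of the baseline geometric mean). About 10%, 16% and 22% of placebo values survive at the three dilution SDs. A true measured difference of +26.1 or +29.6 (log-SD 0.5 or 0.7) shrinks to +4.4 or +3.7. At 0.3 it could not be estimated, because some runs kept too few values. The cut-off is arbitrary; the result shows only that selection on the value can hide a difference.

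**The case against.** The case for leaving the plan alone has real force.

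- The trial is randomised and blinded, and both arms receive the same 50 mL infusions. Dilution that varies alike in both arms cannot bias the difference. This stands: bias needs urine concentration to differ by arm, and nothing in the document shows that it will. It is not excluded either, because the earlier antepartum trial reported an effect on creatinine clearance (Section 4).
- The sentence in Section 9.7.1 covers BUN, serum creatinine and urine electrolytes together, so it could mean each analyte at its own scheduled times. That is a fair reading, but it is not stated, and stating it is half of the fix.
- The text never says that raw concentrations from spot specimens will be used, and Section 9 leaves detail to a separate SAP. Uncorrected concentration is an inference, though the natural one. A SAP can define a ratio; it cannot recover later values that were never captured.
- The capture rule refers to clinical findings, not abnormal electrolyte values, and such findings are recorded as adverse events. There may be no later numbers to average at all. That makes a later summary no more usable.
- Fractional excretion, an obvious remedy, equals excretion divided by serum concentration times creatinine clearance, so it moves with filtration as well. This stands, and it argues against making fractional excretion mandatory or dropping the measured values.

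A reader might infer that the marker will show dilution and selective capture instead of drug effect. The document does not support that: screening and 24-hour values are scheduled for every woman, subject to a feasibility qualifier, and under randomisation dilution is mainly noise.

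**Conclusion.** The point holds as a cheap improvement. As written, the comparison is noisier than it needs to be, and it is open to bias if treatment or co-treatment changes urine concentration. The time points after 24 hours would yield either nothing or a selected subset.

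The impact is minor. The outcome is a descriptive item among the other maternal outcomes in the safety section. The primary endpoint and the key secondary endpoints, serum creatinine and pulmonary edema, are unaffected. The noise ratio of 1.7 to 4.3 and the shift of 20 to 24 rest on assumed variances and an assumed dilution difference; the document supplies neither. The mismatch between scheduled collection and promised time points rests on the text alone, apart from how the time-point wording is read.

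**What to change.** In Section 9.7.1 and the SAP:

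1. Limit the between-arm summary of urine electrolytes to the change from screening to 24 hours after the first dose, and report the number of women with both values.
2. List any later standard-of-care values without summarising them by arm.
3. Add the ratio of each electrolyte to urine creatinine, and its change, alongside the measured concentrations.
4. Treat fractional excretion as optional. If it is reported, note that it also depends on filtration and on serum creatinine, which may be changing at 24 hours.

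The cost is a sentence or two and a derived variable, with no new samples or visits. Women without a urine creatinine value will have no ratio, which is a further reason to keep the measured concentrations.

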9.7.2 Other Fetal/Infant Outcomes of Special Interest

Newborn outcome data, including sex, will be collected at birth and 36 weeks (± 1 week) corrected gestational age including:

- Status at birth (i.e., stillborn or alive)
- NICU stay (number of days)
- Infant exam (weight, length, head circumference)
- Retinopathy of prematurity (Stage ≥ 3)
- Bronchopulmonary dysplasia
- Hypoxic ischemic encephalopathy
- Cystic periventricular leukomalacia
- Sepsis, late onset
- PDA – details of PDA condition and treatment should also be captured.
- Previously unrecognized anomalies (e.g., including, but not limited to, ASD and VSD).
- Respiratory distress syndrome
- Other conditions of prematurity as outlined in [Appendix 4](#)
- Status at 36 weeks (± 1 week) corrected gestational age (i.e. alive or expired, hospitalized or discharged)
- Intrauterine growth restriction
- Blood transfusion receipt and any available related information (e.g., hemoglobin and hematocrit levels prior to transfusion and within 24 hours of transfusion, and NPO status)

9.8 Concomitant Medications

Concomitant medications will be listed by major therapeutic class, but no formal analyses will be performed. Further categorization into more specific categories may be done for select therapeutic classes of medications.

9.9 Study Reports

The following reports will be generated:

- Bioanalytical method validation report for the measurement of AMAG-423 in human blood
- Bioanalytical study report for the measurement of AMAG-423 in human blood
- Immunogenicity method validation report
- Immunogenicity study report

An integrated clinically study report will be generated in ICH format.

10 ETHICAL AND REGULATORY CONSIDERATIONS

10.1 Regulatory Compliance

This study will be conducted in accordance with Good Clinical Practice (GCP) requirements described in the current revision of ICH Guidelines and all applicable regulations, including current United States CFR, Title 21, Parts 50, 54, 56, and 312 and Title 45, Part 164. Compliance with these regulations and guidelines also constitutes compliance with the ethical principles described in the current revision of the Declaration of Helsinki. This study will also be carried out in accordance with local legal requirements.

10.2 Institutional Review Board (Ethics Committee)

The protocol and informed consent form will be reviewed and approved by an IRB (ethical committee) before subjects are screened for entry. The IRB will comply with applicable regulations defined in the United States CFR, Title 21, Part 56 and Good Clinical Practices: Consolidated Guideline (E6), ICH.

Amendments to the protocol will be subject to the same requirements as the original protocol. The Investigator will submit all periodic reports and updates as required by the IRB. The Investigator will inform the IRB of any reportable adverse events or reportable protocol violations.

